RATIONALE & BACKGROUND	
Ciprodiazole (Ciprofloxacin & Metronidazole) is active against a broad spectrum of obligate anaerobic bacteria, including Bacteroids Species (spp.), Fusobacterium spp., Clostridium spp., Treponema spp. and various anaerobic cocci. The action is trichomonocidal, and bactericidal. So, it is indicated in the treatment of Pelvi-abdominal infections caused by gram negative bacteria such as E. coil, Pseudomonas aeruginosa, Proteus mirabilis, Klebsiella pneumonia, Bacteroides fragilis or others.
 
In this study, we compare the safety and efficacy of oral Ciprodiazole 500 mg (Ciprofloxacin /Metronidazole) versus currently used Ciprofloxacin Tablets & Metronidazole tablets in pelvi-abdominal infections and following IV antibiotics in post-operative period, for pelvi-abdominal surgeries or acute conditions

RESEARCH QUESTION & STUDY OBJECTIVES	
Primary Objectives:
 
1) Primary Safety:
 
To compare safety of oral Ciprodiazole ® tablets (Ciprofloxacin/Metronidazole) versus currently used Ciprofloxacin Tablets & Metronidazole tablets for pelvi-abdominal infections, either non-operative or post-operative following IV antibiotics.

	
2) Primary Efficacy:
 
To compare efficacy of oral Ciprodiazole ® tablets (Ciprofolxacin/Metronidazole) versus currently used Ciprofloxacin Tablets & Metronidazole tablets for pelvi-abdominal infections, either non-operative or post-operative following IV antibiotics.
 
Secondary Objective
 
1) Secondary Safety:
 
 - Presence of any signs/symptoms of post-operative wound infection such as redness, fever or wound discharge. - Presence of undesirable effects on total leukocyte count and liver enzymes (SGOT & SGPT) 
2) Secondary Efficacy:
 
 - To compare the complete resolution or improvement of Pelvi-abdominal infection between ciprodiazole® versus combined treatment, based on pelvi-abdominal ultrasound and others - To compare the days for complete healing of post-operative wounds between ciprodiazole® versus combined treatment

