VARIABLES	
Primary Endpoints:
 
1- Primary Safety:
 
 - Incidence of serious/non-serious adverse events 
2- Primary Efficacy:
 
 - Complete resolution for pelvi-abdominal infection based on pelvi-abdominal ultrasound and others and/or clinical response - Complete healing of the of post-operative wounds 
Secondary Endpoints:
 
1- Secondary Safety:
 
 - Presence of any signs/symptoms of post-operative wound infection such as redness, fever or wound discharge. - Change in Total Leukocyte count and Liver enzymes (SGOT, SGPT) between baseline (visit 1) to End of study visit (Follow up 2 V) 
2- Secondary Efficacy:
 
 - Describe complete resolution, improvement, failure or relapse of pelvi-abdominal infection based on pelvi-abdominal ultrasound and others and/or clinical response - Days for complete healing of post-operative wounds after 8 days of treatment (Follow-up 1 V) & 15 days of treatment (End of study visit) between the 2 groups
ASSESSMENT SCHEDULE	
Subjects will be enrolled for 12 months including screening visit
 
 ➤ Visit 1: Screening and treatment initiation visit, Day 0 ➤ Follow-up 1 visit: Day 8 (+/-) 3 days ➤ Follow-up 2 visit & End of study visit: Day 15 (+/-) 3 days
DATA SOURCES	All visits' assessments will be kept in the source files for each patient and in Case Report Form (CRF), which will be verified by the responsible Clinical Research Associate (CRA).
STUDY SIZE	312 patients with pelvi-abdominal infection and/or who started IV antibiotics in post-operative period, for pelvi-

	
abdominal surgeries. They will be randomized by computer, into 2 treatment groups; Ciprofloxacin[®] tablets (Ciprofloxacin/Metronidazole) versus currently used Ciprofloxacin Tablets & Metronidazole tablets, from the surgical department in Menoufia University Hospital and some patients might be referred from other departments in Menoufia University Hospital such as and not limited to; the department of Gynecology and Obstetrics

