4. Disease progressions which requires discontinuation of the study medication or results in inability to continue to comply with study procedures.
5. Consent withdrawn by subject.
6. Lost to follow up
7. SAE or death
8. If a female subject becomes pregnant
9. Subjects which have Cholecystitis and it will be operated upon.

The reason for withdrawal will be recorded in the CRF. If the participant is withdrawn due to an adverse event, the investigator will arrange for follow-up visits or telephone calls until the adverse event has resolved or stabilized.

10.2.4 Assessments to be done:

1- Screening Visit Assessments:

- The enrollment period will be 12 months including the screening visit. Screening assessments will be completed and treatment will be initiated within visit 1.
- During this visit, patients will be screened for fulfillment of the inclusion and exclusion criteria and written informed consent will be obtained.
- Screening assessments will include physical examination, medical history, patient demographics, vital signs, concomitant medications, safety laboratory tests

(including Fasting Blood Sugar (FBS), Total leukocyte count, Liver enzymes (SGOT & SGPT), Total Bilirubin and S. Creatinine), Child-Pugh Score (for hepatic impairment) and, β -HCG (for females of child bearing potential only) and pelvi-abdominal Ultrasound & others.

- Presence of any signs/symptoms of post-operative wound infection such as redness, fever or wound discharge will be recorded (in case of post-operative subjects)

2- Follow-up 1 Visit:(Day 8):

- On-treatment assessments include physical examination, vital signs, AEs, SAEs, concomitant medication and study drug dosing compliance
- Days for complete healing will be checked
- Complete resolution, improvement, failure or relapse of Pelvi- abdominal infection
- Presence of any signs/symptoms of post-operative wound infection such as redness, fever or wound discharge will be recorded (in case of post-operative subjects)

3- Follow-up 2 Visit & End of study visit (Day 15):

- Assessments include physical examination for vital signs, AEs, SAEs, concomitant medication, and study drug dosing compliance
- Pelvi-abdominal Ultrasound and others will be done, if needed upon Physician's decision.
- Days for complete healing will be checked
- Complete resolution, improvement, failure or relapse of Pelvi- abdominal infection

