10.7.6 Primary Safety analysis

A. Number of participants experiencing Serious Adverse Events (SAEs). [Time Frame: visit 1 to End of study visit].

- Frequency distribution (number & percent) of occurrence of SAEs necessitating a change or discontinuation of treatment. Chi² test will be used to determine *p*-value and significance between the 2 groups.
- Frequency distribution (number & percent) of type and severity of SAEs. Chi² test will be used to determine *p*-value and significance between the 2 groups.

B. Number of participants experiencing Adverse Events (AEs) leading to permanent discontinuation of the study drug. [Time Frame: visit 1 to End of study visit].

- Frequency distribution (number & percent) of causes of treatment discontinuations. Chi² test will be used to determine *p*-value and significance between the 2 groups.
- Frequency distribution (number & percent) of occurrence of AEs necessitating a change or discontinuation of treatment. Chi² test will be used to determine *p*-value and significance between the 2 groups.

- Frequency distribution (number & percent) of type and severity of AEs. Chi² test will be used to determine *p*-value and significance between the 2 groups.

10.7.7 Primary Efficacy analysis:

A. Complete resolution for Pelvi- abdominal infection based on pelvi-abdominal Ultrasound

- Frequency distribution (number & percent) of complete resolution for pelvi-abdominal infection. Chi² test will be used to determine *p*-value and significance between the 2 groups.

B. Complete healing of the post-operative wounds [Time Frame: Follow-up 1 V to End of study visit].

- Frequency distribution (number & percent) of complete healing of the post-operative wounds. Chi² test will be used to determine *p*-value and significance between the 2 groups.
- Frequency distribution (number & percent) of incomplete healing of the post-operative wounds. Chi² test will be used to determine *p*-value and significance between the 2 groups.
- Frequency distribution (number & percent) of no healing of the post-operative wounds. Chi² test will be used to determine *p*-value and significance between the 2 groups.

10.7.8 Secondary Safety analysis:

A. Presence of any signs/symptoms of post-operative wound infection such as redness, fever or wound discharge [Time Frame: visit 1 to End of study visit].

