12.2 Patient Enrollment

After signing the informed consent form, each potential subject will be screened for eligibility based on the inclusion and exclusion criteria specified. Randomization will be done.

All visits will occur as closely as possible to the scheduled visit dates with window of 3 days. In case of a premature discontinuation of the study, the subject, will be, if possible called in for a last visit. Even if the subject would not be able to attend, the 'End of Study' forms will be completed .

12.3 12.3 Schedule of visits

Table 1: Schedule of Visits

Observation	Visit 1 (Screening & treatment)	(Follow-up 1 V)	(Follow-up 2 V) End of Study
Time lines	Day 0	Day 8	Day 15
Informed consent document signed	X		
Review Inclusion/Exclusion criteria	X		
Patient Demographics	X		
Significant medical history and current disease status	X		
Physical examination	X	X	X
Vital Signs	X	X	X
Child-Pugh Score	X		
Concomitant medications	X	X	X
Safety Laboratory Tests:			
FBS	X		
Total Leucocytic count	X		X
SGOT (ALT)	X		X
SGPT (AST)	X		X
Total Bilirubin	X		X
S. Creatinine	X		X
Serum β -HCG: (for females in childbearing period)	X		
Pelvi-abdominal Ultrasound & others (Optional)	X		X
Study Drug Dispensed	X	X	
Drug Accountability		X	X

Observation	Visit 1 (Screening & treatment)	(Follow-up 1 V)	(Follow-up 2 V) End of Study
Time lines	Day 0	Day 8	Day 15
Presence of any signs/symptoms of post-operative wound infection such as redness, fever or wound discharge. (in case of post-operative subjects)	X	X	X
Days for complete healing		X	X
Complete resolution, improvement, failure or relapse of pelvi - abdominal infection		X	X
AE		X	X
SAE		X	X
Study Completion Form			X

The subsequent visits will occur as follows :

- **Visit 1 (Screening & treatment initiation Visit):** Day 0
- **Follow-up V1:** Day 8 (+/-) 3 days
- **Follow-up V2 & End of Study Visit:** Day 15 (+/-) 3 days

12.3.1 Visit 1 (Screening & treatment initiation):

- During this visit, subjects will be informed about the study. If they are willing to participate in the study, they will sign the written ICF. A copy of the signed ICF will be given to the subject. In addition, the subjects will be evaluated for study eligibility according to the inclusion and exclusion criteria.
- Screening Assessments will include: physical examination, vital signs, demographic data (Age & Gender), medical history and concomitant medications.

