9.4.2 Primary Efficacy

Table 9 *Number and percent of complete resolution for pelvi- abdominal infection among treatment groups*

	Group A (N=156)	Group B (N=156)	p-value
No of complete resolution for pelvi-abdominal infection, N (%)			
No of incomplete resolution for pelvi-abdominal infection, N (%)			

Table 10 *Number and percent of complete healing of the post-operative wounds among treatment groups*

	Group A (N=156)	Group B (N=156)	p-value
Complete healing, N (%)			
Incomplete healing, N (%)			
No healing, N (%)			

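### Primary resolution has no named analysis visit, and Protocol 12.3.2 may close out Day 8 resolvers before the scheduled Day 15 assessments

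*Protocol*

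**What the plan says.** **Endpoint and analysis.** The synopsis, Protocol 10.3.1 and SAP 5.1.2 define the primary infection endpoint as "Complete resolution for pelvi-abdominal infection based on pelvi-abdominal ultrasound and others and/or clinical response". The analysis headings in Protocol 10.7.7 A and SAP 8.7 A read "Complete resolution for Pelvi- abdominal infection based on pelvi-abdominal Ultrasound". The analysis bullet under each heading is "Frequency distribution (number & percent) of complete resolution for pelvi-abdominal infection", compared by a chi-squared test. Neither the heading, the bullet nor SAP Table 9 names a visit.

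**Scans.** Table 1 marks ultrasound at Visit 1 and Day 15, labels the row optional, and marks nothing at Day 8. For Day 15, Protocol 10.2.4 says "Pelvi-abdominal Ultrasound and others will be done, if needed upon" the physician's decision, and 12.3.3 also makes it conditional on need. No post-baseline scan is required.

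**Visits.** Resolution, improvement, failure or relapse is recorded at both follow-up visits (10.2.4, Table 1, 12.3.2, 12.3.3). The synopsis gives the first as "Follow-up 1 visit: Day 8 (+/-) 3 days" and puts the same window around Day 15.

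**Close-out.** Protocol 12.3.2, on the Day 8 visit, says that in case of complete resolution the end-of-study labs are taken and the End of Study Form is completed. The same list asks subjects to return at Day 15 and states no exception for resolvers.

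**The concern.** The plan records the primary outcome twice and does not say which record is analysed. The choice could then be made after open-label data have been seen.

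The close-out clause adds a second problem. If it is followed, the patients who could relapse have no scheduled visit at which relapse would be found, although relapse has its own test in 10.7.9. They also have no scheduled questioning about new adverse events after Day 8, although adverse-event incidence is the primary safety endpoint. Their leukocyte and liver-enzyme values would be Day 8 values pooled with Day 15 values from everyone else. How long a patient is followed would depend on an efficacy judgement made by staff who know the treatment.

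**Working it through.** The plan states no figure on this point to reproduce. The check compares passages and does arithmetic on the visit windows.

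**1. Basis of the outcome.** Three endpoint statements allow a clinical basis; two analysis headings mention ultrasound only. The bullets under those headings carry no scan condition. SAP Table 9 has two rows, complete resolution and "No of incomplete resolution for pelvi-abdominal infection, N" (%), under columns of N=156, with no row for patients not scanned. The sample-size section (10.5.1) cites overall clinical resolution rates (74% and 63%). All of this points to the heading being shorthand for the endpoint, but the text does not say so.

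**2. Which visit counts.** Under three rules that the text permits:

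| Day 8 | Day 15 | Day 8 status | Day 15 status | Resolved at either visit |
|---|---|---|---|---|
| resolved | resolved | yes | yes | yes |
| resolved | relapsed | yes | no | yes |
| not resolved | resolved | no | yes | yes |
| not resolved | not resolved | no | no | no |
| resolved, closed out | no visit | yes | missing | yes |

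The second, third and fifth patterns change with the rule. Wound healing (10.7.7 B, SAP 8.7 B) does carry a time frame, but it runs from Follow-up 1 to the end-of-study visit. It spans the same two visits and leaves the same question open.

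**3. Does a Day 8 resolver return?**

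- For early exit: the last bullet of 12.3.2. In partial support, the opening line of 12.3.2 says Day 8 may be the end of treatment for some, and 10.1 links the 15 days of follow-up to the end of treatment.
- For Day 15: the return instruction in 12.3.2; the synopsis, with 15 days of follow-up from enrolment and no qualifier; Table 1, which places the Study Completion Form and all post-baseline labs at Day 15 only; 12.3.3, which calls Day 15 the end-of-study visit; and 10.3.2 and SAP 5.2.1, which tie the lab change to Follow-up 2.

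Most of the text favours Day 15. No sentence overrides the 12.3.2 bullet.

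**4. Windows** (synopsis, plus or minus 3 days).

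- Day 8 visit: 8 − 3 = 5 to 8 + 3 = 11.
- Day 15 visit: 15 − 3 = 12 to 15 + 3 = 18.
- An unspecified analysis visit therefore spans Days 5 to 18.
- Nominal time without a scheduled assessment after a Day 8 close-out: 15 − 8 = 7 days; 7/15 = 0.467, or 47%.
- Difference in timing of end-of-study labs between a closed-out patient and any other: at least 12 − 11 = 1 day, at most 18 − 5 = 13 days.

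**The case against.** **The ultrasound wording is a drafting slip.** Largely accepted. A reader might infer that the primary outcome exists only for patients whom the physician chose to scan. The bullets, SAP Table 9 and all three endpoint statements speak against that. What stands is that the heading should match the endpoint.

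**One bullet against the whole schedule does not show that follow-up will be lost.** Correct. A reader might infer that resolvers will be sent home at Day 8, but the documents show only an unreconciled instruction. It still needs settling, because site staff follow the visit list.

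**Adverse events are not lost.** Also correct in part. Section 13.2 collects them at each contact and to the end of the study and a post-treatment period, and gives patients a number to call at any hour. The later sentence ruling out active follow-up for new events does not make clear which period it means, so it proves little. What a close-out would remove is the scheduled Day 15 questioning.

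**Making Day 15 decisive could do harm.** This stands. Efficacy is analysed only in patients who completed without violation (10.7.1, SAP 8.1). A Day 8 resolver who does not return could be classed as a deviation and leave the primary analysis. The fix has to deal with this.

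**Day 15 status is a preference; resolution at either visit would also be a rule.** True. Day 15 is proposed because the either-visit rule would count a recorded relapse as a success. Naming the visit also does not supply criteria for complete resolution.

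**Conclusion.** Two points hold. No passage fixes which visit's status is the primary resolution outcome, and 12.3.2 contradicts the Day 15 end of study set out elsewhere. Both should be settled before database lock.

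The size of any bias is unknown. The documents give no scan rate, early-exit rate or adverse-event rate, and bias is zero if scanning and early exit are unrelated to arm. What can be stated is the exposure per closed-out patient: nominally 7 of 15 days without a scheduled assessment, and labs 1 to 13 days out of step with other patients.

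A reader might scale this up: 0.74 × 156 = 115 patients per arm, and 115.4 × 7 / (156 × 15) = 35% of scheduled follow-up days. That is a ceiling, not an estimate. It assumes that every patient has an infection, although post-operative patients are also enrolled. It borrows 74% from a cited study of complicated infections, assumes that every resolution is reached by Day 8, and assumes that every resolver is closed out. It measures lost scheduled follow-up, not bias.

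**What to change.** **Analysis visit and heading**

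- In Protocol 10.7.7 A and SAP 8.7 A, replace the heading with the endpoint's own wording, leaving the endpoint unchanged.
- State that the Day 15 (end-of-study) status is analysed and that relapse by Day 15 counts as not resolved.
- Name the visit also in Protocol 10.7.9 A, SAP 8.9 A and SAP Tables 9 and 15.
- State which visit's status counts for wound healing in 10.7.7 B and SAP 8.7 B.

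**Close-out**

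- Reconcile 12.3.2 with 10.1, 10.3.2, Table 1 and 12.3.3, so that Day 8 resolvers, whether or not treatment has ended, still attend the scheduled Day 15 visit for status, adverse events and labs.
- State that a Day 8 resolver who misses Day 15 is not removed from the primary efficacy analysis for that reason alone. Settle how the missing status is handled together with the per-protocol-only efficacy population (10.7.1, 14.2, SAP 8.1).

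**Cost.** Wording changes in both documents; Protocol 10.7.2 already foresees a final SAP before database lock in which differences are documented. Early responders attend one visit that is already in the schedule. Treatment and scanning do not change, and clinical status remains an open-label judgement.

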10.5.1 Determination of Sample Size

As the primary objective is to assess the safety of oral Ciprodiazole[®] tablets (Ciprofolxacin /Metronidazole) versus currently used Ciprofloxacin Tablets & Metronidazole tablets following IV antibiotics in post-operative period, for pelvi-abdominal surgeries, and based on the previous study "Comparison of Intravenous/Oral Ciprofloxacin Plus Metronidazole Versus Piperacillin / Tazobactam in the Treatment of Complicated Intra-abdominal Infections".^[15] Overall clinical resolution rates were statistically superior for CIP+MET (74%) compared with PIP/TAZO (63%). Mean length of stay was 14 days for CIP1MET and 17 days for PIP/TAZO patients.

So, the following parameters are used to calculate the expected sample of the study:

- Design: non-inferiority
- Sample Size = 312 Subjects (1:1)
- Ciprodiazole Sample Size (Experimental group) = 156 subjects
- Current used regimen Sample Size (Control group) = 156 subjects
- Confidence level 95% (α error = 5%)
- Power = 80%
- Non-Inferiority margin = 2%

10.5.2 Sample Size & Treatment Groups:

Total of 312 Egyptian patients who have pelvi-abdominal infection or started IV antibiotics in post-operative period, for pelvi-abdominal surgeries will be enrolled in the study and randomized, using a computer system, with a ratio of 1:1, into two categories as follows:

1. Group will receive Ciprodiazole[®] tablets; 156 patients
2. Group will receive Ciprofloxacin Tablets & Metronidazole tablets; 156 patients

10.5.3 Randomization:

Subjects will be randomized into the two treatment groups with a balanced ratio of 1:1. Randomization by block Computer-generated randomization lists will be established by Data Management department (DM) of CRO (Nagy Research). The number of patients of the two treatment groups will be balanced (ratio 1:1). (156 Ciprodiazole[®]: 156 Ciprofloxacin Tablets & Metronidazole tablets).

A document describing the procedure of constitution of the randomization lists will be stored confidentially at Nagy Research CRO

Block size: 2, 4

The Randomization list will be done using website:
(<https://www.sealedenvelope.com/simple-randomiser/v1/lists>)

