10.7.3 Analysis variables

Descriptive Analysis:

- Descriptive analysis of the collected data. All enrolled patients will be included in the safety analysis.
- All quantitative primary and secondary end point variables will be described
- Data from primary and secondary endpoints will be summarized using appropriate summary statistics i.e. n (number of subjects), mean, Standard Deviation (SD), median and range.

Comparative Analysis:

- All tests will be performed on the 5% level of significance.
- Chi² test for unpaired categorical variables.
- Paired t-test to estimate the change in numerical variables throughout the study visits.
- Student t-test to estimate the comparison between the subgroups for the numerical variables.
- *P*-values less than 0.05 will be considered statistically significant

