- Presence of any signs/symptoms of post-operative wound infection such as redness, fever or wound discharge will be recorded (in case of post-operative subjects)
- Child-Pugh Score will be calculated for liver impairment and pelvi-abdominal Ultrasound and others will be done
- Lab results will be checked for: (Fasting Blood Sugar (FBS), Total leukocytes count, liver enzymes (SGOT & SGPT), Total Bilirubin and S. Creatinine), and Serum β -HCG for females of child bearing potential only
- The Investigator will keep a log of all subjects, who will sign the ICF. Even if the subject would not pass the screening, his/her signed consent form will be retained

in the Investigator file and will be considered as screening failure. The reason(s) for screen failure will be recorded in the screen failure form in the screening log.

- All data related to screening visit must be reviewed (signed and dated) by the Investigator to ensure that the subject will be eligible for the study, before dispensing the study drug.
- Randomization will be done and subjects will be administered the study products; either Ciprofloxacin® tablets or Ciprofloxacin Tablets & Metronidazole tablets.
- Study products sufficient for the next 7 days will be supplied; either Ciprofloxacin® tablets or Ciprofloxacin Tablets & Metronidazole tablets, and storage conditions will be explained. Study products supplied will be recorded.
- Subjects will be asked to come after 7 days of treatment and bring the empty blisters of medication received, with window of 3 days.

In case of any premature discontinuation of the study, the subject will be, if possible, called in for a last visit. Even if the subject was not able to attend the last visit, the End of Study Form must be completed.

Child-Pugh Score will be recorded, as follows:

The score employs five clinical measures of liver disease. Each measure is scored 1-3, with 3 indicating most severe derangement.^[20]

Table 2: Child-Pugh Score

Measure	1 point	2 points	3 points
Total bilirubin, µmol/l (mg/dl)	<34 (<2)	34-50 (2-3)	>50 (>3)
Serum albumin, g/dl	>3.5	2.8-3.5	<2.8
Prothrombin time, prolongation (secs)	<4.0	4.0-6.0	> 6.0
Ascites	None	Mild	Moderate to Severe
Hepatic encephalopathy	None	Grade I-II (or suppressed with medication)	Grade III-IV (or refractory)

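### Complete wound healing, a primary efficacy endpoint, is compared without using the wound-infection signs recorded at Visit 1; the test stays valid but gives up some precision at no saving (minor)

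*Protocol*

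**What the plan says.** Complete healing of post-operative wounds is one of two primary efficacy endpoints (Protocol 10.3.1, SAP 5.1.2). Its planned analysis in Protocol 10.7.7 B and SAP 8.7 B is: "Frequency distribution (number & percent) of complete healing of the post-operative wounds. Chi² test will be used to determine" a p-value between the two groups. The general methods in Protocol 10.7.3 and SAP 8.3.2 offer only "Chi² test for unpaired categorical variables" for such outcomes. Neither document names a covariate or a stratified method.

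The Visit 1 procedures in Protocol 12.3.1 include: "Presence of any signs/symptoms of post-operative wound infection such as redness, fever or wound discharge will be recorded (in case of post-operative subjects"). This item is listed ahead of randomisation and of the first supply of study drug. In the analysis the signs appear only as a secondary safety outcome (Protocol 10.7.8 A, SAP 8.8 A).

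Four further points bear on the issue:
- Randomisation uses blocks of 2 and 4, with no stratification factor stated (Protocol 10.5.3, SAP 7.3).
- SAP Tables 1 to 3, which describe the arms at baseline, have no row for wound-infection signs. Table 11 has no visit column, so a baseline difference would not be displayed.
- SAP Table 10, for healing, is headed N=156 per arm, although the trial also enrols patients with infections and no operation.
- Protocol 10.5.1 states "Design: non-inferiority" and "Non-Inferiority margin = 2" per cent, beside clinical-resolution rates from a cited study. It gives no wound-healing rate.

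**The concern.** A wound that already shows redness or discharge when treatment starts is plausibly less likely to be fully healed by Day 15. If so, part of the variation in the primary healing outcome can be explained by something measured before randomisation. A crude comparison leaves that part in the error term, and nothing in the randomisation balances it. The stake is efficiency: a wider confidence interval than the same patients could give, on an endpoint whose sample is smaller than the trial total, because only post-operative patients have wounds and efficacy is analysed per protocol only (Protocol 10.7.1, SAP 8.1). A reader of the report would also be unable to see whether the arms began with similar wounds.

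**Working it through.** **The plan's own figure.** Protocol 10.5.1 gives non-inferiority, a 2% margin, 5% alpha (sidedness not stated), 80% power and 156 per arm. Taking 74% for the experimental arm, 63% for control and one-sided 5%:

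n = (1.645 + 0.842)² × (0.74×0.26 + 0.63×0.37) / (0.11 + 0.02)² = 6.18 × 0.4255 / 0.0169 ≈ 156 per arm, or 312 in total.

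So 312 is reproduced. The calculation rests on clinical-resolution rates and does not involve wound healing.

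**Inputs for the precision check.** All are assumptions, because the documents give none of them. Overall healing p = 74% is borrowed from the clinical-resolution rate. Let q be the share of wounds with signs at Visit 1, and d the drop in healing probability when signs are present. The number of post-operative patients per arm is shown as 156 (every patient post-operative) and 78 (half of them).

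**Formulas.**
- Crude SE of the arm difference = √(2p(1−p)/n).
- Share of outcome variance explained by the signs = q(1−q)d² / (p(1−p)). This is the variance reduction from adjustment, and it does not depend on n.
- Adjusted SE = crude SE × √(1 − variance reduction).
- SD of the movement in the crude difference caused by chance imbalance in signs = d × √(2q(1−q)/n).

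With p(1−p) = 0.74×0.26 = 0.1924, the crude SE is √(0.3848/156) = 4.97 points, or √(0.3848/78) = 7.02 points.

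| Assumed q, d | Healing without / with signs | Variance reduction | Equivalent extra patients | Adjusted SE, n=156 / n=78 | Imbalance SD, n=156 / n=78 |
|---|---|---|---|---|---|
| 10%, 20 points | 76% / 56% | 0.0036/0.1924 = 1.9% | 2% | 4.92 / 6.96 | 0.7 / 1.0 |
| 20%, 30 points | 80% / 50% | 0.0144/0.1924 = 7.5% | 8% | 4.78 / 6.76 | 1.4 / 1.9 |
| 30%, 40 points | 86% / 46% | 0.0336/0.1924 = 17.5% | 21% | 4.51 / 6.38 | 2.1 / 2.9 |

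Allowing q from 5% to 30%, d from 20 to 40 points and other overall healing rates, the variance reduction runs from about 1% to 20%.

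**Simulation check of the middle row** (40,000 runs, Mantel-Haenszel risk difference): the SE falls from 4.98 to 4.80 points at 156 per arm and from 7.02 to 6.76 at 78 per arm, variance reductions of 7.0% and 7.3%.

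**Where chance imbalance sits.** For the middle row at 78 per arm, 6.76² + 1.92² = 45.6 + 3.7 = 49.3 = 7.02². The imbalance movement is one component of the crude standard error. It is not an addition to it.

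**The case against.** The strongest reply is that nothing is wrong with the planned test. Under randomisation the chi-square keeps its type I error, chance imbalance is already inside its standard error, and the gain may be as little as 2%. All of that stands, and it limits the point to efficiency. One qualification is fair: validity is an average over randomisations. If the arms happened to differ by 2 SDs in Visit 1 signs, the crude two-sided 5% test would reject a true null about 7.6% of the time in the middle scenario and 10.9% in the strong one. Adjustment removes that dependence, but it does not make the unconditional test wrong.

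Two stronger readings are tempting, and the documents support neither.

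First, a reader might infer that imbalance in infected wounds can move the result by about the whole 2-point margin. A 1-SD movement is anywhere from 0.7 to 2.9 points in the table, depending on unstated inputs. The crude SE of 5.0 to 7.0 points is already 2.5 to 3.5 times the margin. The margin is not tied to healing, and no planned test uses it.

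Second, a reader might put a baseline-outcome correlation of 0.5 into the sample-size inputs and conclude that power rises from 80.1% to 89.1%. That requires 156 post-operative patients in each arm. With 78, the same formula gives 54.6% and 65.1%. It also borrows an 11-point advantage from a comparison with piperacillin/tazobactam, whereas both arms here contain ciprofloxacin and metronidazole. At equal true rates of 74%, 156 per arm and one-sided 5%, power is 10.7% crude and 11.9% adjusted. Moreover, the planned chi-square, like a stratified Cochran-Mantel-Haenszel test, tests zero difference, so non-inferiority power does not describe either.

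It can also be said that fever may reflect the abdominal infection and not the wound. That may weaken the covariate but does not disqualify it: it need only be recorded before randomisation. The objection that the signs exist only for post-operative patients is correct, and the fix must respect it.

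**Conclusion.** The point holds as a minor, cost-free improvement. The primary healing comparison ignores a pre-randomisation measure of the same wounds, the randomisation does not balance it, and the planned tables would not show it. The crude test remains valid; the loss is precision. Its size is not determined by the documents: about 2%, 7.5% or 17.5% of the variance in the three scenarios, all resting on an assumed 74% healing rate and assumed prevalence and prognostic strength. If the signs turn out not to predict healing, the gain is close to nil. Adjustment does not turn the comparison into a non-inferiority test and does not make a 2-point margin attainable; those are separate matters.

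**What to change.** In Protocol 10.7.7 B and SAP 8.7 B, restrict the healing comparison to post-operative patients in the efficacy population. Make the primary analysis of complete healing a risk difference with its confidence interval, stratified by Visit 1 wound-infection signs (any versus none) with Mantel-Haenszel weights. A standardised risk difference from a logistic model with treatment and Visit 1 signs would serve equally; choose one in advance. If a p-value is kept, use the matching stratified test and state that it tests zero difference.

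In SAP Table 10, keep the crude counts and percentages as descriptive rows and replace N=156 with the number of post-operative patients analysed in each arm. Without that change, patients with no wound could be counted as having no signs. Add Visit 1 signs by arm to the baseline tables.

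The cost is a few sentences of SAP text, one stratified analysis and a table row. The data are already on the visit schedule. Protocol 10.7.2 and SAP 8.2 provide for a final SAP before database lock that documents differences, so the change can be pre-specified there.
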